## **Accelerated Weaning**

**USUAL CARE** 

**Pre-NIV**: arterial or capillary blood gas required showing pH<7.35, PaCO2>6.5kPa ("NIV-decision blood gas" for NIVO score and minimisation criteria). Provide brief participant information sheet.

**Confirm ready to wean**: After 24+ hours of NIV, 60-minute trial of unsupported breathing with arterial or capillary blood gas at the end ("qualifying blood gas" for inclusion criteria & randomisation).

**Recommence NIV** at the end of 60-minute unsupported breathing trial.

Recruit: confirm all eligibility criteria met, provide full participant information and obtain consent.

#### Randomisation

Step 1

4-hour trial off NIV, target SpO2 88-92%, PtcCO2 monitoring\* in situ

Assess respiratory rate# (over 1 minute), SpO2, FiO2 and PtcCO2: a) once stable 10-30 minutes, and b) 4 hours after NIV removal

Take arterial blood gas at the end of the 4-hour trial off NIV

Step 2

Arterial blood gas result

If pH ≥ 7.35 remain off NIV

PtcCO2 monitoring remains in place for a further 8 hours\*

NIV is removed from the bed space

If pH < 7.35 replace NIV

Return to step 1 to repeat daily 4hour trials off NIV until the arterial blood gas after 4 hours off NIV is satisfactory\*

ISRCTN: 64639614 IRAS: 313485 CPMS: 53277

\*Repeat ABG if there is a substantial clinical deterioration or an increase in PtcCO2>1 kPa from the start of each period (4 hr trial post NIV removal, 8 hr monitoring post NIV discontinuation), that persists despite correction of any transient reasons for deterioration (e.g. coughing, mucus plugging). The presence or absence of other clinical features that would independently trigger a repeat ABG must be documented (oxygen desaturation, raised respiratory rate, symptoms etc).

\*Respiratory rate should be observed and counted over 1 minute.

Step 1 and 2 happens same day. Target SpO2 88-92% at all times when on and off NIV.

IRAS: 313485 CPMS: 53277

#### 9. Adverse Event and Serious Adverse Event Reporting

Adverse events and serious advert event report forms have been developed specifically for the Trial. All serious adverse events will be reported to the Chief Investigator and investigated within 1 week of their occurrence.

The following definitions will be used:

#### Adverse event (AE)

An AE is any untoward medical occurrence in a participant whilst taking part in the trial; which does not necessarily have to have a causal relationship with the assessment being undertaken.

An AE can therefore be any unfavourable and unintended sign (including an abnormal laboratory finding), symptom or disease temporally associated with the assessment, whether or not considered related to the diagnosis and treatment.

#### Serious adverse event (SAE)

An SAE is an adverse event that:

- Results in death
- Is life-threatening, or places the participant at immediate risk of death from the events as it occurred
- Requires or prolongs hospitalisation
- · Causes persistent or significant disability or incapacity
- Is another condition which investigators judge to represent significant hazards

Note: The term "life-threatening" in the definition of "serious" refers to an event in which the participant was at risk of death at the time of the event; it does not refer to an event which hypothetically might have caused death if it were more severe.

- Resulted in a permanent impairment of a body structure or a body function
- Required in-patient hospitalisation or prolongation of existing hospitalisation
- Resulted in medical or surgical intervention to prevent permanent impairment to a body structure or a body function
- Other important medical events\*

\*Other events that may not result in death, are not life threatening, or do not require hospitalisation, may be considered a serious adverse event when, based upon appropriate medical judgement, the event may jeopardise the patient and may require medical or surgical intervention to prevent one of the outcomes listed above.

#### Exacerbation of COPD (ECOPD)

ECOPD is a clinical diagnosis made when a patient with COPD experiences a sustained (e.g. 48 h+) increase in cough, sputum production, and/or dyspnoea. It commonly occurs in the cohort of patients under investigation in this study, who are at high risk of developing an ECOPD and indeed 20% will be readmitted to hospital within 28 days of being discharged (when the primary reason for admission was ECOPD). The Chief Investigator and Principal Investigator therefore deem ECOPD to be an expected AE and SAE. In the event of a participant developing an ECOPD, this will be captured as an outcome, but not reported as an AE.

ISRCTN: 64639614 IRAS: 313485 CPMS: 53277

In the NIVO study, of the patients who survived to discharge 51.2% were readmitted within 90 days from discharge. This timeframe is very close to the follow up period of this trial. The Chief Investigator, with the support of the Sponsor, therefore deems that ECOPD leading to readmission or death are expected events and will be reported to the DMC, TSC and sponsor, but not regarded as SAE's to be reported to REC or HRA.

Death during the index admission will be reported as a SAE to the DMC, TSC, sponsor, REC and HRA.

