#### 3.4 Secondary outcomes

- 1. Relapse requiring NIV (defined as recurrent AHRF>48 hours after removal of ventilator).
- 2. Total duration of ventilation.
- 3. Length of hospital stay.
- 4. NIV complications (incidence and severity).
- 5. Patient reported outcome measures: Modified Borg dyspnoea scale\*; Sputum clearance via visual analogue scale\*; Richards-Campbell sleep questionnaire\*; Hospital Anxiety and Depression Scale (HADS) pre-discharge; St Georges Respiratory Questionnaire for COPD (SGRQ-C) and EQ-5D-5L days 7, 30 and 90 post-randomisations.
- 6. Mortality in-hospital and 90-days post-randomisation.
- 7. Readmissions 30-days post-discharge.
- 8. Health economic analysis:
  - Costs to the NHS in terms of provision of the interventions (both on a respiratory support unit and a critical care unit) and cost implications of subsequent resource utilisation up to 90 days follow up;
  - Cost utility analysis using EQ-5D-5L quality adjusted life years (QALYs).
- 9. Responder analysis within the accelerated weaning group to identify predictors of success/failure.
- \*Day 1 to 5.

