### 4. Trial Design

A multi-centre, open-label, parallel, randomised controlled trial.

Our position is one of equipoise. The randomised controlled trial design will provide a definitive result as to the better outcome for patients: a) a standard wean may provide a longer duration of NIV wean, with lower PaCO2 at discharge, with less relapse and readmissions; or b) an accelerated wean may mean a shorter duration of NIV wean, but with more relapse requiring NIV, and more readmissions.

IRAS: 313485 CPMS: 53277

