#### Reporting of AEs

All AE's occurring during the study observed by the investigator or reported by the participant, whether or not attributed to the assessments being made will be recorded on the source document worksheet as specified in the protocol. The following information will be recorded: description, date of onset and end date, severity, assessment of relatedness to assessments and/or intervention, action taken and information should be provided as necessary.

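### ECOPD is exempted from adverse event reporting as a captured outcome, but no such outcome is listed, so ECOPD without readmission and readmissions after day 30 have no comparison by arm

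*Protocol*

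**What the plan says.** The protocol's section 9, under Exacerbation of COPD (ECOPD), makes four statements about these events:

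- The investigators class ECOPD as expected, whether it counts as an AE or as an SAE.
- "In the event of a participant developing an ECOPD, this will be captured as an outcome, but not reported as an AE".
- ECOPD leading to readmission or death is expected and "will be reported to the DMC, TSC and sponsor, but not regarded as SAE's to be reported to REC or HRA".
- A participant who dies before leaving hospital is treated differently: that is a full SAE, sent to all five bodies.

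The same section gives the background rates used to justify this: 20% readmitted within 28 days of discharge, and 51.2% of those surviving to discharge in the NIVO study readmitted within 90 days.

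Under Reporting of AEs, the items recorded for each AE include an "assessment of relatedness to assessments and/or intervention". Section 3.4 lists nine secondary outcomes. The one closest to ECOPD after discharge is "Readmissions 30-days post-discharge", with no cause specified. Section 4 names the possible price of the accelerated wean as a shorter wean "but with more relapse requiring NIV, and more readmissions".

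**The concern.** The exemption has one stated justification: the event will be picked up elsewhere, as an outcome. If no such outcome exists, the justification fails and the event falls between two systems. It is not in the AE record, where relatedness would be judged, and it is not in the outcome list, where the arms would be compared.

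This matters because the trial asks whether a shorter wean can be had without loss. A high background rate of exacerbation is a good reason not to send each one to the ethics committee. It does not make an excess in one arm expected, and only a comparison by arm would show such an excess. A statement that accelerated weaning is safe would have nothing to say about the exempted events that no listed outcome covers.

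**Working it through.** **Step 1. Look for the ECOPD outcome.** I checked each place in the protocol where an outcome is listed, collected or scheduled.

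- Section 3.3 (primary): time to successful weaning. Recurrent AHRF needing NIV within 48 hours means weaning has not succeeded. No ECOPD item.
- Section 3.4 (secondary): relapse requiring NIV after 48 hours, ventilation time, length of stay, NIV complications, patient-reported measures, mortality, 30-day readmission, health economics, responder analysis. No ECOPD item.
- Section 7.6, Table 1: exacerbation history is baseline information. The trial outcomes row holds readmissions, mortality and health-service contacts.
- Sections 7.7 and 7.8: daily symptom scales, then questionnaires, spirometry, resource use, readmissions and mortality. No ECOPD item.
- Appendix 1: no ECOPD row.

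So the outcome to which section 9 refers is not defined, collected as such, or scheduled.

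**Step 2. See what existing outcomes cover.** Section 9 defines ECOPD by a sustained increase in cough, sputum or breathlessness. Relapse in section 3.4 requires recurrent AHRF needing NIV. The definitions overlap only in part.

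- Recurrent AHRF needing NIV within 48 hours: compared, through the primary outcome.
- Relapse after 48 hours: compared.
- Readmission to 30 days after discharge: compared. Section 10.3.3 states that readmission is captured only for that period.
- Death in hospital and to 90 days: compared.
- ECOPD treated by a GP or in A&E without admission: cost data only (section 10.9).
- Worsening in the index admission that does not need NIV: no ECOPD item records it. The resource diary starts at discharge.
- Readmission after day 30 post-discharge and up to day 90 post-randomisation: cost data, and for ECOPD readmissions a report to the DMC, TSC and sponsor.

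**Step 3. Length of the uncovered window.** For a participant discharged d days after randomisation, the readmission outcome closes at day d + 30 and follow-up ends at day 90. The gap is 90 − (d + 30) = 60 − d days. The protocol gives no expected stay. For illustration, d = 5 gives 55 days and d = 10 gives 50.

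**Step 4. Rough number of readmissions in the gap.** Live discharges are taken as between 164 (all survive) and 164 × (1 − 0.054) = 155. The latter borrows the 5.4% competing risk of death from section 10.1, which is a figure at 65 hours and so only a stand-in.

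- By day 28: 0.20 × 155 = 31 to 0.20 × 164 = 33.
- By day 90: 0.512 × 155 = 79 to 0.512 × 164 = 84.
- Between: (0.512 − 0.20) × 155 = 48 to (0.512 − 0.20) × 164 = 51.

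The roughly 31 to 33 early readmissions fall inside the 30-day outcome and are compared. The later 48 to 51 are not.

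**Step 5. Relatedness and timelines.** Relatedness is listed only among the items recorded for an AE. Section 9 calls ECOPD an expected AE and SAE, says it is not reported as an AE, and says that ECOPD readmission or death is "not regarded as SAE's to be reported to REC or HRA". The SAE definition includes any AE that requires or prolongs hospitalisation, and the SAE procedure requires every SAE to reach the chief investigator and host organisation within one working day. From these statements a site cannot tell whether an ECOPD readmission needs a relatedness judgement or falls under the one-working-day rule.

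**The case against.** The strongest case on the other side is that the harms that matter most are already compared. Section 4 names relapse and readmission as the possible price of the accelerated wean, and both are listed outcomes. Recurrence within 48 hours is in the primary outcome, and mortality is compared in hospital and to 90 days. This stands. A reader might infer that the main harm of early NIV withdrawal has no planned comparison. The documents do not support that. It would require treating recurrent AHRF as the same thing as ECOPD, and the definition in section 9 is symptomatic, without acidaemia.

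A reader might also infer that ECOPD readmissions and deaths escape safety oversight, or that the DMC hears of them only at scheduled meetings and without causality information. Neither is stated. These events go to the DMC, TSC and sponsor; death in the index admission is a full SAE to all bodies; and the protocol sets neither timing nor content for the DMC reports. The waiver can be read as applying only to the REC and HRA. The REC in any case receives only related and unexpected SAEs.

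It can further be said that ECOPD, being called an expected AE, might still be recorded on the worksheet with relatedness and merely not be reported. That reading is possible, but the text does not say so.

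Finally, contacts after discharge are collected: section 10.9 provides a diary of COPD and non-COPD treatment, calls at days 30 and 90, and a check against NHS records. An SAP, which is not at hand, could tabulate them. That makes the repair easy. It does not supply the missing outcome, because section 9 relies on one that the protocol's own list omits, and section 10.3.3 limits readmission to 30 days.

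**Conclusion.** The point holds in a limited form. Section 9 exempts ECOPD from AE reporting on the strength of an outcome that the protocol does not contain. Two groups of events are therefore left without a comparison by arm: ECOPD that does not lead to readmission, and readmissions from day 30 after discharge to day 90 after randomisation. ECOPD kept off the AE record has no stated relatedness assessment, and the reporting duty for ECOPD readmissions and post-discharge deaths is unclear. The primary analysis is not affected.

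The figure of about 48 to 51 later readmissions is an order of magnitude only. It rests on these assumptions:

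- Both rates apply to this low- and medium-risk population. The 51.2% comes from the NIVO study; the 20% is cited separately, so their difference may mix populations.
- Day 28 stands in for day 30.
- The 51.2% runs to 90 days after discharge, which is later than day 90 after randomisation, so the number within follow-up would be lower.
- No cause is given for the 51.2%, and the protocol does not state the ECOPD share.

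ECOPD treated without admission is additional, and the protocol gives no rate for it.

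**What to change.** 1. Add to section 3.4 a secondary safety outcome of ECOPD and readmission to 90 days post-randomisation, compared by arm, and carry it into Table 1, section 7.8 and Appendix 1. The source is the diary, the day-30 and day-90 calls and the NHS-record check already planned in section 10.9. Because the diary begins at discharge, the definition should say whether worsening during the index admission counts and, if so, where it is recorded. The call form needs a field that identifies a contact as ECOPD. Amend the statement in section 10.3.3 that readmission is captured only within 30 days.

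2. Reconcile the ECOPD text in section 9 with the SAE definition, the AE recording items and the SAE procedure in the same section. A site should be able to tell whether relatedness is recorded for ECOPD, and whether the one-working-day report applies to ECOPD readmissions and post-discharge deaths. Which rule to adopt is for the sponsor.

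The cost is wording, a field on an existing form and one more table. Two cautions go with it. Community events are self-reported in an open-label trial and need cautious interpretation. The comparison should also be presented as an estimate with its interval: with 82 per arm and a 90-day rate of 51.2% in both, the standard error of the difference is √(2 × 0.512 × 0.488 / 82) = 0.078, so the 95% interval is about ±15 percentage points (1.96 × 0.078 = 0.153). It would show a large excess but could not exclude a moderate one.

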#### Reporting of AEs

All AE's occurring during the study observed by the investigator or reported by the participant, whether or not attributed to the assessments being made will be recorded on the source document worksheet as specified in the protocol. The following information will be recorded: description, date of onset and end date, severity, assessment of relatedness to assessments and/or intervention, action taken and information should be provided as necessary.

#### Reporting procedure for all SAEs

All SAEs need to be reported to the Chief Investigator and Host Organisation (Northumbria Healthcare) within one working day of the investigator team becoming aware of them. Reports of related and unexpected SAEs will be submitted to Research Ethics within 15 days of the Chief Investigator becoming aware of the event, using the Northumbria Healthcare SAE report form.

All reporting to Northumbria Healthcare R&D will be by email ([contact]) giving as much information about the incident as possible, and should be signed by the PI or Co-investigator.

#### Risks and discomforts

It will be necessary to perform arterial blood gas analysis, as would be part of routine clinical care. This may be temporarily uncomfortable for the patient for the duration of the procedure. All staff performing arterial blood gases will be trained to do so according to local policy.

#### 10. Statistics and Data Analysis

#### 10.1 Sample size calculation

The sample size has been estimated using patient-level data from the 10-centre validation cohort within our NIV Outcomes study.

We selected patients meeting the inclusion criteria for the proposed RCT, and derived weaning time as defined in the protocol. Two sites were evidently not adhering to the standard weaning protocol and therefore were excluded. This provides the best available data on weaning time within standard care in the proposed RCT (median t=2.71 days).

The total study duration from first subject first visit to last subject last visit is 27 months. The cumulative incidence rate for the competing risk of death is the same for both treatment strategies, which is 5.4% at the time of interest, t=2.71 days or 65 hours. This chosen time corresponds to the cumulative incidence rate of the 50% for the event of interest (successful weaning) in standard care. We assume that weaning time might be achieved 1 day (24

hours) earlier in the accelerated weaning arm, thus, to reduce the median weaning time from 2.71 to 1.71 days the incidence rate in the new treatment must be equal to 0.667.

The other important statistical indices we use here are the critical alpha 5%, power 80%, two-sided, and we assume the sample size in both groups are the same. The sample size we obtained was 164 (82 for each group with expected number of events in the new treatment is 69 and in the standard treatment is 67). All calculations were done in nQuery 8.7. The total sample size reported includes 10% attrition or drop out.

#### 10.2 Planned Recruitment Rate

Participating sites have estimated recruitment based on prior activity levels. Anticipated rate of recruitment: 8 patients per month (across 7 centres). Anticipated duration of recruitment: 24 months.

The physical measures to limit spread of COVID-19 were also associated with a reduction in admissions for ECOPD, primarily due to a reduction in spread of other respiratory pathogens and consequent exacerbations, rather than fear of attending hospital. It is unclear whether exacerbations will fully return to previous levels; some people with severe COPD may continue to take precautions. We will assess admission rates for ECOPD requiring NIV in the run up to and during the trial. Individual site recruitment to target will be closely monitored. If there are concerns we will seek to expand sites at an early stage. We will be recruiting patients whilst acutely unwell. Fortunately, our PPI work showed most would consider participation. We have detailed additional measures to support recruitment (including early identification, multiple methods of providing information, and support to overcome communication barriers, including poor health literacy).

#### 10.3 Statistical Analysis Plan

The statistical plan has been designed by the Research Design Service and the co-applicant Statistician.

#### 10.3.1 Summary of baseline data and flow of patients

We will assess baseline comparability of the randomised groups, including but not limited to the variables listed in Table 2.

Table 2. Baseline variables and reporting methods.

Variable	Form of data	Reporting method
Age (years)	Continuous	Mean (SD)
Sex (male/female)	Nominal	%
Smoking burden (pack years)	Continuous	Median (IQR)
FEV1 (% predicted)	Continuous	Mean (SD)
eMRCD	Ordinal	Median (IQR)
Long-term oxygen therapy (yes/no)	Nominal	%
Previous ECOPD requiring admission (yes/no)	Nominal	%
Previous admission requiring NIV (yes/no)	Nominal	%
Pre-NIV pH	Continuous	Median (IQR)
Pre-NIV PaCO 2	Continuous	Median (IQR)
Pre-NIV HCO 3 -	Continuous	Mean (SD)
Pre-randomisation pH	Continuous	Median (IQR)
Pre-randomisation PaCO 2	Continuous	Median (IQR)
Pre-randomisation HCO 3 -	Continuous	Mean (SD)
PEARL	Ordinal	Median (IQR)

ISRCTN: 64639614 IRAS: 313485 CPMS: 53277

We will produce a consort flow diagram to detail patients not eligible for the trial.

#### 10.3.2 Primary outcomes analysis

Primary outcome: the competing risks (CR) approach will be used to compute cumulative incidence of successful weaning as the first event of interest, and death as a competing risk. The Fine-Gray subdistribution hazard model will be fitted to compare both groups while adjusting for covariates (hospital site; NIV Outcomes score; and independent predictors of weaning time identified in a post-hoc analysis of the equivalent subpopulation within the NIV Outcomes study).

#### 10.3.3 Secondary outcome analysis

For all outcomes (both primary and secondary) we will present the characteristics, including those stratified by the weaning strategies. We will describe all baseline characteristics, follow-up measurements using suitable measures of tendencies: means and median with the associated standard deviation, 95% confidence interval and interquartile ranges for continuous variables and frequency and proportions for categorical variables (including binary variables). We will use Chi-Square test (or Fisher's Exact test in case of small number of observations) if the variable is categorical and will use t-test if the variable is continuous. For variables that are not parametric we will use Mann-Whitney U test. We will use the critical alpha 5% (thus p-value < 0.05 will be considered statistically significant) and we will also present the 95% confidence interval. Analyses will be performed by intention to treat, with secondary analyses of primary and secondary outcome based on protocol adherence. All analyses will be done in  $R^{15}$  and SPSS.  $R^{16}$ 

All baseline patient characteristics and outcomes will be included in the imputation mode. Mean change in quality of life over 90 days (SGRQ-C, EQ5D5L) from baseline will be calculated. In-hospital and 90-day mortality, and readmission within 30-days: time from discharge to death and time to readmission will be analysed using a Cox proportional hazards regression model, adjusted for covariates. For this analysis, no interaction between interventions will be assumed. Analysis will be two-sided at 5% level. We will also report the model performance by C-statistic. A sensitivity analysis will be performed with the log-rank test stratified by the centre. As we are only capturing readmission within 30 days, we will compare the proportion adjusted for the covariates (In-hospital mortality=NIVO; Readmission=PEARL: previous admission, extended MRC Dyspnoea scale, age, left and right heart failure).

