#### 3.3 Primary outcome

Time to successful weaning: duration from the baseline ABG confirming selection criteria are met, to final removal of the ventilator. Weaning will be considered successful when there has been no recurrence of AHRF requiring replacement of NIV within 48 hours of discontinuation of NIV. Recurrent AHRF more than 48 hours after removal of the ventilator will be considered relapse. Death precludes weaning and will be captured in a competing risk analysis.

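### Length of stay would be compared by t-test or Mann-Whitney with early deaths counted as short stays, which misleads if mortality differs between arms and deaths come early

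*Protocol*

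**What the plan says.** Section 3.4 lists "Total duration of ventilation" and "Length of hospital stay" as secondary outcomes 2 and 3. No model is named for either. The general rule in Section 10.3.3 therefore applies: the plan "will use t-test if the variable is continuous", and "For variables that are not parametric we will use Mann-Whitney U test". The same section states "Analyses will be performed by intention to treat", with secondary analyses based on protocol adherence. The only time-to-event model it names among the secondary outcomes is for mortality and readmission: "time from discharge to death and time to readmission will be analysed using a Cox proportional hazards regression model".

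For the primary outcome the protocol takes a different line. Section 3.3 says "Death precludes weaning and will be captured in a competing risk analysis", and Section 10.3.2 estimates the "cumulative incidence of successful weaning as the first event of interest, and death as a competing risk", followed by a Fine-Gray model. Nowhere does the protocol say what value of stay or ventilation time a patient who dies in hospital should receive.

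**The concern.** Death ends a hospital stay as surely as discharge does, but it is not the same result. If all randomised patients enter a t-test or rank test with their observed days, a patient who dies on day 2 contributes a 2-day stay and ranks with the quickest recoveries. The protocol recognises this problem for weaning and deals with it there; the general rule does not carry that handling over to stay.

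At stake is how a secondary result would be read in one particular situation. The trial asks whether less ventilation is safe. If accelerated weaning led to more early deaths, the stay comparison could move in its favour because of them. Dropping the deaths would not cure this, since it compares survivors only and survival is determined after randomisation.

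**Working it through.** **1. Which test reaches length of stay.** It is a continuous secondary outcome with no model of its own, so the rule in Section 10.3.3 covers it. Intention to treat keeps patients who die in the comparison, and no other value is assigned to them, so their observed days are used. This follows from applying the rule; the protocol does not say it in words.

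**2. How many deaths to expect.** The protocol gives no figure for stay that could be reproduced. The related planning figure is in Section 10.1: 5.4% dead by 65 hours in each arm, so 82 × 0.054 = 4.4 per arm. Section 2 quotes 9.2% inpatient mortality for COPD patients on NIV in the investigators' own service, so 82 × 0.092 = 7.5 per arm. The 9.2% is not specific to low- or medium-risk patients who are ready to wean. Roughly 4 to 8 deaths per arm is therefore a working range.

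**3. Size of the shift in means.** Suppose recovery is identical in both arms, survivors stay a mean of S days, and deaths occur at a mean of D days. With mortality p1 and p0, the spurious difference in mean stay is

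(p1 − p0) × (S − D).

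It is zero if mortality is equal or if D = S.

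**4. Chance of a significant test.** Assumptions, none from the protocol: survivors' stay Gamma with shape 2 and mean 10 days, deaths Gamma with shape 2 and the mean shown, 82 per arm, no true effect, two-sided 5%, at least 4,000 simulated trials per row.

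| Mortality | Mean day of death | Spurious shorter stay (days) | Mann-Whitney significant |
|---|---|---|---|
| 15% v 5% | 3 | 0.10 × 7 = 0.70 | about 12% |
| 15% v 5% | 6 | 0.10 × 4 = 0.40 | about 7% |
| 15% v 5% | 10 | 0.10 × 0 = 0 | about 5% (nominal) |
| 10.8% v 5.4% | 3 | 0.054 × 7 = 0.38 | about 7% |
| 8% v 8% | 3 | 0 | 4.9% (nominal) |

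In the first row the t-test is significant in about 10% of trials.

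**5. Sensitivity to the assumed distribution.** A second set of assumptions was tried: survivors' stay lognormal with median 8 days and log-SD 0.7, deaths between 0.5 and 4 days.
- At 10.8% v 5.4% mortality, Mann-Whitney favours the arm with more deaths in 7.5% of trials, against a nominal 2.5%.
- At 18.4% v 9.2%, the figure is 14.9%.
- Ranking deaths worst in the same data reduces these to 0.7% and 0.2%.
- With equal mortality (5.4% or 9.2% in both arms), total rejections stay near 5%.

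**6. Ventilation time.** The same rule applies, but no distortion was calculated. Planned median weaning times are 2.71 and 1.71 days (Section 10.1). A patient ventilated until death on day 2 or 3 may therefore rank near or above the median rather than among the shortest.

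**The case against.** The strongest reply is that Section 10.3.3 names neither outcome, says nothing about deaths, and may be completed by an analysis plan that is not shown. It is true that the protocol does not state that death is a good result, and an analysis plan could add an exception. But this is more than silence: the protocol fixes a test and an analysis population, and together they produce the problem unless something overrides them. That also sits badly with the protocol's own handling of death for weaning.

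The second reply is that the planning assumption is equal mortality (Section 10.1), under which nothing is tilted, and that deaths late in the stay do little harm. This stands and limits the point. Section 10.6 allows for a look at survival if a substantial difference arises; that is a contingency and does not show that one is expected. Mortality is also reported as an outcome, so excess deaths would be visible, although that does not correct a misleading stay comparison.

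Three stronger readings are tempting, and the documents do not support them:
- **That the bias would carry into the cost case.** Section 10.9 costs the resources actually used, by intention to treat. Bed-days used by patients who die belong there, and these tests are not part of it.
- **That ventilation time is distorted to the same degree.** This was not quantified, and the planned weaning times make it doubtful.
- **That about 14 of 164 patients would die before weaning.** This needs constant hazards carried beyond 65 hours: 82 × 0.054/0.554 + 82 × 0.054/0.721 = 8.0 + 6.1. The protocol itself states only 5.4% at 65 hours, or about 9 of 164.

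**Conclusion.** The point holds in limited form. As written, the general rule would score an early in-hospital death as a short stay, while the protocol treats death as a competing event for its primary outcome. The resulting tilt needs two conditions together: unequal mortality, and deaths earlier than typical discharge. Under the assumed stays it ranges from nothing (equal mortality, or deaths at about the usual time of discharge) to a spurious 0.7 days and about 12% significant tests (15% v 5%, deaths at mean 3 days). A doubling of the planned 5.4% gives about 7%. These sizes depend on stay and death-time distributions that the protocol does not supply. Severity is low to moderate, because the outcomes are secondary and few deaths are expected, but the error would favour accelerated weaning in just the case where it caused early deaths.

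**What to change.** Exempt length of stay from the general rule in Section 10.3.3. Compare it as time from randomisation to discharge alive, with in-hospital death as a competing event, using the cumulative incidence and Fine-Gray framework of Section 10.3.2. Show raw days in hospital as description and keep them for costing.

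Keep total duration of ventilation as the listed outcome, but make the between-arm comparison one in which death is not favourable. Two options are final removal of NIV alive during the index admission with death competing, or a rank test with deaths ranked worst. Give raw hours on NIV as description. Limiting this to the index admission matters: NIV status is recorded daily during admission (Section 7.7), and dates of NIV use after discharge are not clearly collected, so a fixed window running past discharge might not be supported.

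The cost is a few sentences of analysis wording, settled before outcomes are seen. Discharge date and time, NIV removal date and time, and mortality are already in Table 1 (Section 7.6). The sample size rests on the primary outcome and does not change. The small downside is that the results are less familiar than mean days, so descriptive medians should stand beside them.
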